STUDY PROTOCOL

“Morbidity of Conventional and No-touch Saphenectomy in Coronary Artery Bypass Grafting, a Randomized Non-inferiority Clinical Trial”

MD. [name]
CI: [name]
Cel: [name]
Address: [name].
Email: [contact]
Instituto Nacional de Cirugía Cardíaca.
July 5th, 2024.

Summary:

A clinical research project will be carried out, it consists of a non-inferiority study. The objective is to compare the morbidity of two different surgical techniques for the extraction of the internal saphenous vein, intended to be used as a conduit in coronary bypass.

Current clinical trials have shown that the no-touch saphenectomy technique has had a positive impact on the short- and long-term patency of coronary bypass, compared to the conventional extraction technique. It is important to highlight that the conventional technique is the most used in our country (Uruguay, South America), while the "no touch" has fallen into disuse.

Given this disparity in the application of the techniques, it is considered essential to compare both methods in terms of morbidity. For this purpose, a prospective randomized clinical trial will be carried out. The primary objective will be to investigate the non-inferiority of the "no touch" technique compared to the conventional technique, specifically focusing on postoperative morbidity of the surgical site. This morbidity will be defined and measured in terms of local infection, hematoma, flictenes, secretions, necrosis, wound dehiscence, paresthesias, pain and functional impotence.

Introduction:

The internal saphenous vein, as an inverted free graft, has been one of the most commonly used conduits to perform coronary bypass in myocardial revascularization surgery since 1967. Over the years, various dissection techniques for this vein have been described, which include the conventional one with continuous or sectional incisions, the "no touch" and the endoscopic route.

The patency of the venous conduits tends to decrease significantly over time. One year after surgery, around 10% of venous bypasses are occluded; the occlusion rate increases 1% to 2% annually over the next 1 to 6 years, and increases 4% annually for 6 to 10 years postoperatively. Ten years after surgery, up to approximately 50% of vein grafts are occluded.

On several occasions, research has been carried out on the factors that influence the patency of these grafts, such as the quality and run-off of the native vessels, the harvesting technique and the patient's risk factors.

Currently, the most widely used technique remains the conventional one, which involves a continuous incision in the skin of the leg or thigh. In this technique, a dissection of the subcutaneous tissue surrounding the vein is performed, the collaterals are ligated, and the free venous duct is sectioned. The length of the conduit varies depending on the amount of bypass to be performed.

The "no touch" technique, proposed by Domingos S.R. Souza in 1996, despite having demonstrated superiority in bypass patency according to several studies, it is not the most commonly used nowadays. A randomized controlled trial showed better graft patency in the short and medium term, as well as less intimal hyperplasia when using the "no touch" technique compared to conventional extraction. From a technical point of view, this methodology implies avoiding all direct contact with the venous duct. The vein is removed with perivascular tissue acting as protection against manipulation-induced damage, thus preserving endothelial nitric oxide synthase activity. This results in effective protection against vasospasm, eliminating the need for overdistention. The adventitia and structures within the surrounding tissue pedicle possess mechanical and functional properties that protect against spasm and ischemia, while preventing the phenomenon known as kinkin. Despite these demonstrated advantages, the "no touch" technique faces limited adoption compared to conventional vein stripping in coronary bypass surgery.

There are not many relevant randomized clinical trials that compare the morbidity of this technique with the conventional one. In this context, we consider it crucial to evaluate whether there are significant differences in terms of wound morbidity in the mid-postoperative period (1 week), late (1 month) and long-term postoperative period (6 months).

We will define each variable previously: it will be considered to have a local infection when the wound shows signs of flow and it has been necessary to start antibiotic treatment, hematoma when there is a tumor or abnormal hardening caused

by the accumulation of blood, blisters when a skin blister appears on the wound that contains watery substances and not pus, secretions when the wound secretes a liquid (serous, bloody, purulent), necrosis when there is a necrotic plaque in the wound larger than 10 x 10 mm, dehiscence of the wound when the suture loses continuity, paresthesia when there is a tingling sensation due to an irritative sensitivity disorder, pain when it is located at the level of the wound and functional impotence when it prevents or limits ambulation.

Revision:

According to current literature, patency at 16 years of venous bypass using the conventional technique is 64%, compared to 83% achieved with the "no touch" technique. This last index even resembles the Gold-standard represented by the internal mammary artery. Although it has been shown that the "no touch" technique preserves numerous properties of the vein, favoring a longer duration of its patency, the conventional technique continues to be the preferred one in clinical practice. This technique is recognized as a Class IIa recommendation in the 2018 European Society of Cardiology and European Association for Cardiothoracic Surgery myocardial revascularization guidelines.

Existing studies have focused their attention on evaluating the patency of the ducts; however, there is a lack of solid information on the morbidity associated with this technique in the lower limb of patients. During the extraction of the saphenous vein using the "no touch" technique, it is sectioned with the perivascular adipose tissue and the saphenous nerve of the leg, therefore, it is of great interest for us to evaluate the incidence of the postoperative complications, previously mentioned, and compare these results with those obtained through the conventional technique.

A single-center randomized clinical trial was published in 2014, in Canada, carried out by Domingos S.R. Souza and Stephen E. Fremes. This study demonstrated significant differences in leg morbidity at 3 months, favoring the conventional technique, although this difference did not persist at one year. An important limitation was the small number of participants, with only 17 patients. In order to overcome this limitation, we intend to carry out a study with a larger sample of patients.

In 2021, another multicenter randomized clinical trial was published in China, led by Shengshou Hu, which included a considerable number of patients, 2,638 in total. This study not only compared patency at 1 year, but also wound morbidity. Significant differences between both techniques were identified before hospital discharge, such as an increase in exudate, numbness and edema in patients undergoing the "no touch" technique, but the difference was not maintained after one year. It is relevant to note that no serious complications, such as necrosis or compartment syndrome, were recorded in any of the patients. Regarding pain rates, no significant differences were observed at three months or one year. Furthermore, multivariate analysis revealed that female sex, diabetes, and hypertension were independent predictors of wound complications. These findings provide valuable information for understanding the long-term results of both techniques.

Objectives:

Our primary objective will be to demonstrate the non-inferiority of the "no touch" technique over the conventional technique in terms of wound morbidity in patients undergoing coronary revascularization, within a non-inferiority margin. Defining morbidity as the combined result of local infection, hematoma, blisters, secretions, necrosis, wound dehiscence, paresthesias, pain and functional impotence.

We sought to achieve as a specific objective the incidence of each of the study factors: local infection, hematoma, blisters, secretions, necrosis, wound dehiscence, paresthesias, pain, functional impotence and then compare them between both groups at different times.

The anatomopathological study of some of the saphenous vein preparations, one "no touch" and the other conventional, will also be carried out using optical microscopy and ultrastructural comparisons using transmission electron microscopy.

Additionally, patients will be offered computed tomography angiography every year to evaluate graft patency.

Through multivariate analysis, the relationship with independent factors will be analyzed.

Null hypothesis: "no touch" saphenectomy is inferior to the conventional technique.

Alternative hypothesis: "no touch" saphenectomy is not inferior to the conventional technique.

Methodology:

The design corresponds to a single-center, open, non-inferiority, controlled, randomized clinical trial. The trial will be blind for the patient and to the investigator that will evaluate the morbidities in the postoperative time, only the surgeon knows which technique is used.

The target population will be those over 18 and under 70 years of age, undergoing coordination coronary revascularization surgery, in which it is necessary to use the internal saphenous vein as a conduit. Those who do not meet the entry criteria, emergency surgeries, patients with poor metabolic control ($\text{HbA1c} > 6.5\%$), chronic venous insufficiency or chronic obstructive arteriopathy of the lower limbs, and type II obesity ($\text{BMI} > 35$) will be excluded.

Given that the number of patients assigned to each group is required to be similar throughout the study, the randomization method that we believe is most appropriate is assignment through permuted block randomization of four.

Evaluations will be carried out in person before discharge from the hospital, approximately one week after the operation. Subsequently, in-person assessments will be conducted at the one-month follow-up, and finally, telephone assessments will be conducted at six months. The assessment will be carried out by researchers who are blind to the randomization group and will record on a form, indicating the presence (1) or absence (0) of the following aspects: local infection requiring antibiotics, hematoma, blisters, secretions, necrosis and dehiscence of the wound. . As for the rest of the variables, such as paresthesias, pain and functional impotence, they will be recorded according to the pain scale from 0 to 10.

The data of each patient will be grouped into tables, including relevant personal history and answers to the questionnaires. The analysis will then be carried out from these forms using the corresponding analytical tests.

A monitoring and safety committee will be appointed that will continuously evaluate adverse effects (included in the primary objective) as well as clinical results (operative and 1-year mortality) and will consider suspension of the study in the event of a significant increase.

Sample calculation:

A probability of complication of saphenectomy by conventional or "control" technique of 10% was assumed, based on studies from our institution, and according to preliminary studies we expect to find 50% more in the "no touch" technique, therefore 15%. To determine the non-inferiority margin, 10 patients who were recently revascularized, 5 men and 5 women, were asked how many times more pain or local infection they were willing to accept with the "no touch" technique in exchange for greater bypass patency. short and long term. When analyzing the results, it is obtained that they would be willing to accept up to twice as many complications by applying the "no touch" technique, therefore the non-inferiority limit will be 20%. With these values, assuming a 95% confidence interval and a power (1 - beta) of 80%, and taking into account a probable 20% of lost patients, we can calculate the necessary population sample size, which was in total 52 patients; 26 people in the group with conventional technique and 26 in the "no touch".

Informed consent:

Two informed consents have been prepared that cover details about the research, its duration and relevance, the procedure to be performed, as well as the associated risks and benefits. In preoperative evaluations, the surgical team personnel will be responsible for obtaining this consent. In this document, the patient will have the opportunity to express their willingness to participate or not in the research.

Institution:

The study will be carried out at the Instituto Nacional de Cirugía Cardíaca, a medical care institution dedicated to the diagnosis and treatment of cardiovascular conditions, the first institute of cardiac surgery and hemodynamics in the country with more than 50 years of experience. Located at the address [name], SMI Hospital, [contact], email [contact].

Schedule:

The schedule consists of a first stage where the surgeries of the 52 patients will be performed, we estimate 9 months. The second stage will be data collection, 3 controls will be carried out: 7 days after surgery, in the polyclinic approximately one month later, and 6 months later by phone call.

After one year, a coronary CT angiography will be performed to evaluate the patency of the bypasses. The data will be grouped into tables by the team of researchers. The duration of the first stage will be from the first surgery to the last, we estimate that it will be 6 months.

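### Paresthesia and walking limitation enter the primary composite with no preoperative score and no new-onset or harvested-leg requirement, so nothing stops symptoms unrelated to the harvest being counted

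*Combined protocol and SAP*

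**What the plan says.** The Introduction defines each component of the outcome. Paresthesia is counted as "paresthesia when there is a tingling sensation due to an irritative sensitivity disorder", and functional impotence is counted as "functional impotence when it prevents or limits ambulation". Pain, in the same sentence, is restricted to the wound. The Objectives section puts all three in the primary composite.

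Under Methodology, the three symptoms are recorded on a 0 to 10 scale with no cut-off. The first assessment is described thus: "Evaluations will be carried out in person before discharge from the hospital, approximately one week after the operation". The others are at one month in person and at six months by telephone, and the Schedule section lists the same three. Preoperative evaluations appear only under Informed consent, as the occasion for obtaining consent.

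The exclusions that name leg disease are "chronic venous insufficiency or chronic obstructive arteriopathy of the lower limbs". HbA1c above 6.5%, BMI above 35 and emergency surgery are also excluded, and patients must be under 70. Medical history is tabulated, but no rule uses it to discount symptoms that were already present.

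**The concern.** A patient with non-diabetic or well-controlled diabetic neuropathy, a spinal or joint problem, or an old leg injury can be enrolled. After surgery the assessor has no earlier score for separating old tingling or limping from new, least of all by telephone at six months. Events of this kind do not depend on technique, so they add to both arms and dilute the contrast.

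Paresthesia is where this matters most. The Revision section says the saphenous nerve is taken with the no-touch vein and gives that as a reason for studying leg morbidity. The Objectives also compare each component separately, so the dilution reaches that comparison as well as the composite.

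**Working it through.** **Inputs from Sample calculation.** Conventional 10%, no-touch 15%, a limit of 20%, a 95% confidence interval, power 80%, 20% loss, 26 per arm. After loss, 26 × 0.8 = 20.8, taken as 21 per arm. Sidedness is not stated; one-sided 0.05 (z = 1.645) is used, with 0.025 as a check.

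**The plan's own figure.** The total of 52 does not follow from these inputs when complications are treated as harm. With a 20-point margin, n per arm = (1.645 + 0.842)² × (0.10×0.90 + 0.15×0.85) / (0.20 − 0.05)² = 59.8, so 60. A figure near 52 appears only if the expected 5-point harm is entered as a benefit: the denominator becomes 0.25², n = 21.5, so 22 per arm, 44 in total, and 44 × 1.2 = 52.8. That is a separate matter, but it explains why the starting power below is 0.43 and not 0.80.

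**Assumption.** A fraction b of patients in each arm scores positive from symptoms unrelated to the harvest. The documents give no value; 10% to 30% is shown. The planned 10% and 15% are taken as harvest-related rates.

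**Formulas.**
- Observed rate = b + (1 − b)p, so observed difference = (1 − b) × true difference.
- Difference reading: P(declare) = Φ[(0.20 − d)/SE − 1.645], SE = √[p₁(1−p₁)/21 + p₂(1−p₂)/21].
- Ratio reading: P(declare) = Φ[(ln 2 − ln(p₂/p₁))/SE − 1.645], SE = √[(1−p₁)/(21p₁) + (1−p₂)/(21p₂)].

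**Worked case, b = 20%.**
- Planned rates: 0.20 + 0.80×0.10 = 28%, and 0.20 + 0.80×0.15 = 32%.
- 20-point difference at the planned rates: SE = 0.1413; 0.16/0.1413 − 1.645 = −0.513; probability 0.30. Without background symptoms, SE = 0.1018 and the probability is 0.43.
- 20-point difference at the margin: a true 10% v 30% is seen as 28% v 44%, so d = 0.16; SE = 0.1461; 0.04/0.1461 − 1.645 = −1.371; probability 8.5%.
- Ratio of 2 at the margin: a true 10% v 20% is seen as 28% v 36%, ratio 1.29; SE = 0.455; (0.693 − 0.251)/0.455 − 1.645 = −0.674; probability 25%.

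| b | Planned rates as seen | Difference (points) | 20-point reading: power | 20-point reading: false NI | True doubling seen as | Ratio reading: false NI | Ratio reading: chance of NI at planned rates |
|---|---|---|---|---|---|---|---|
| 0 | 10% v 15% | 5.0 | 0.43 | 5.0% | 2.00 | 5% | 10% |
| 10% | 19% v 23.5% | 4.5 | 0.34 | 6.7% | 1.47 | 13% | 20% |
| 20% | 28% v 32% | 4.0 | 0.30 | 8.5% | 1.29 | 25% | 32% |
| 30% | 37% v 40.5% | 3.5 | 0.29 | 10.6% | 1.19 | 40% | 46% |

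(NI = non-inferiority declared; false NI = declared when the truth lies at the margin.)

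**Checks, b = 0 to b = 20%.**
- Exact binomial enumeration, 20-point reading: power 0.46 to 0.33, false non-inferiority 6.6% to 9.0%.
- Exact enumeration with a 0.5 correction, ratio reading: false non-inferiority 6% to 29%.
- One-sided 0.025, 20-point reading: power 0.31 to 0.20, false non-inferiority 2.5% to 4.6%.
- 10-point difference (10% v 20%), one-sided 0.05: false non-inferiority 5.0% to 6.6%.

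**Ceiling reading.** If 20% caps the no-touch rate itself, the planned 15% is seen as 23.5%, 32% or 40.5%, above the cap in every case.

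**The case against.** A reader might infer that the plan instructs assessors to score every old symptom as a complication at every visit. It does not. The Summary speaks of postoperative morbidity at the surgical site, the Objectives of wound morbidity and incidence, and the paresthesia definition requires an irritative sensory cause. A blinded assessor could reasonably leave out a chronic limp. That stands. But these are general labels; with no preoperative score and no attribution rule, they leave the decision to individual judgement.

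A reader might also infer that background symptoms always pull the trial towards non-inferiority. That does not follow. The point estimate is diluted, but the decision rests on a confidence limit, and a higher event rate widens the interval. On the 20-point reading, non-inferiority becomes less likely at the planned rates; only the error at the margin moves the unsafe way. On the ceiling reading the direction reverses. The text does not settle which reading applies: it says "they would be willing to accept up to twice as many complications by applying the 'no touch' technique", which is a ratio, and concludes "therefore the non-inferiority limit will be 20" per cent, without saying of what.

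Other points stand in part:
- The HbA1c, BMI and age limits probably remove some neuropathy and walking limitation, but not all.
- Randomisation balances background symptoms on average. Balance does not prevent dilution of a proportion, and with 26 per arm chance imbalance is plausible.
- If 0 to 10 scores were compared as means, equal additive background would cancel on average and leave only noise. The composite, however, needs each item as present or absent, and with no cut-off it is undefined whether a low chronic score is an event.
- The size is wholly assumed. If the institution's 10% already includes background symptoms, b cannot exceed 10% and the larger figures do not apply.

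**Conclusion.** The concern holds as a gap in outcome definition and baseline measurement. Two components of the primary composite require neither new onset nor the harvested leg, and no preoperative score exists to make the distinction. The true risk difference shrinks by (1 − b): 5 points becomes 4.5, 4.0 and 3.5 at b = 10%, 20% and 30%.

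The consequence for the conclusion depends on a margin the plan leaves unclear. At b = 20%, 21 per arm and one-sided 0.05:
- as a 20-point difference, mainly lost power (0.43 to 0.30), with some rise in false non-inferiority (5.0% to 8.5%);
- as a ratio of 2, a large rise in false non-inferiority (5% to 25%);
- as a ceiling, a result tilted against no-touch.

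These figures rest on the assumed b, on its being equal in both arms, and on every such patient scoring as an event. It should be settled before enrolment, because a preoperative score not taken then cannot be reliably recovered afterwards.

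**What to change.** At the preoperative evaluation that already takes place, score paresthesia and walking limitation on the same 0 to 10 scale, in the leg or legs that may be harvested. Record any leg pain there too, as a reference only.

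In the composite definition, count paresthesia and functional impotence only when they are new or worse than the preoperative score, by a prespecified number of points, in the harvested leg. Apply this at one week, one month and six months. Keep pain as wound-level pain: there is no wound before surgery, so a change-from-baseline rule does not suit it.

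The cost is three extra questions at an existing visit, a sentence in the definition, and a slightly lower composite rate because background symptoms no longer count. No new visit or exclusion is needed, and the stated sample size is not altered by this change.

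### One fixed, published block size of four lets a recruiter who knows all earlier allocations deduce on average 33% of assignments; the share is lower, down to none, if that knowledge is incomplete, and the plan does not say which case applies

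*Combined protocol and SAP*

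**What the plan says.** The Methodology section gives the whole randomisation method in one sentence: "the randomization method that we believe is most appropriate is assignment through permuted block randomization of four". The reason offered is balance: "Given that the number of patients assigned to each group is required to be similar throughout the study". No stratification is described, so a single sequence at one centre is the natural reading. The Sample calculation section sets 26 patients per arm, 52 in all, which is 13 complete blocks.

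On who knows what, Methodology states that "only the surgeon knows which technique is used", and that the patient and the outcome assessor are blind. The Informed consent section adds: "In preoperative evaluations, the surgical team personnel will be responsible for obtaining this consent". The plan does not say who generates or holds the list, how the next assignment is hidden, or whether it is released before or after consent. Reference 16 carries the name Sealed Envelope, but it is a sample-size calculator and not a concealment method.

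The Schedule section gives two accrual periods: "a first stage where the surgeries of the 52 patients will be performed, we estimate 9 months", and later "The duration of the first stage will be from the first surgery to the last, we estimate that it will be 6 months".

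**The concern.** In a block of four with two patients per arm, the fourth place always follows from the first three, and the third follows whenever the first two match. Knowing the size, where each block starts and what was assigned before is enough. The size is printed in the protocol, and those taking consent belong to the same team as the surgeon, who knows the technique used.

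Blinding the patient and the assessor does not help here, because the exposure comes earlier, when someone decides whom to enrol and when. The Revision section reports from a large trial that "female sex, diabetes, and hypertension were independent predictors of wound complications". These factors are visible before consent, although no effect sizes are given and the exclusion of "patients with poor metabolic control" narrows the diabetes contrast. If a foreseeable assignment influences enrolment, the arms can differ in risk in either direction. Lower-risk patients entering no-touch would favour the claim the trial hopes to make.

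Few events are expected. The planning rates of 10% and 15% give 26 × 0.10 + 26 × 0.15 = 6.5 events, or 21 × 0.25 = 5.25 after 20% loss (about 21 per arm). Small imbalances therefore matter. The real count is uncertain because the composite includes items scored 0 to 10 with no stated threshold.

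**Working it through.** The plan states no predictability figure, so there is none to reproduce.

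**1. Certain deductions.** There are 6 equally likely orders of two A and two B, hence 24 places. A place is certain if every order consistent with what is known gives the same arm.

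| Earlier allocations known | Probability certain at places 1, 2, 3, 4 | Average | Of 52 | Best guess right |
|---|---|---|---|---|
| All | 0, 0, 1/3, 1 | 8/24 = 33.3% | 17.3 | 17/24 = 70.8% |
| All but the latest one | 0, 0, 0, 1/3 | 2/24 = 8.3% | 4.3 | 14/24 = 58.3% |
| All but the latest two | 0, 0, 0, 0 | 0% | 0 | 13/24 = 54.2% |

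With none known, the certain share is also 0%. If each earlier allocation is known independently with probability q, the third place is certain with probability q²/3. The fourth is certain with probability q³ + 3q²(1 − q)/3 = q². The average is (q²/3 + q²)/4 = q²/3, which is 8.3% at q = 1/2 and 3.7% at q = 1/3.

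**2. Spread around 33%.** With all earlier allocations known, each block yields one certain place, or two with probability 1/3. Thirteen blocks give 13 to 26 certain places, or 25% to 50% of 52.

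**3. Which row might apply.** Accrual of 52 in 6 or 9 months is one patient per 6 × 30.44/52 = 3.5 days or 9 × 30.44/52 = 5.3 days. Assume that one recruiter learns every allocation at surgery and that consents arrive at random (Poisson). The certain share is then P(0 pending) × 8/24 + P(1 pending) × 2/24. It is 27–29% if consent is 1 day before surgery, 17–22% at 3 days, 7–12% at 7 days and 1–4% at 14 days. The plan does not state this interval.

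**4. Effect on the error that matters (illustration only).** False non-inferiority has to be evaluated with the true difference equal to the margin. The Sample calculation gives a limit of 20%, which can be read as a 20-point difference or as a rate of 20% against 10%, a 10-point margin. These assumptions are not in the documents:
- 26 per arm, with 13 high-risk patients in each.
- High risk is r = 1.5, 2 or 3 times low risk. For arm mean p, low risk = 2p/(1 + r) and high risk = r times that.
- Non-inferiority is declared if the upper two-sided 95% Wald limit lies below the margin.
- A swap replaces one high-risk no-touch patient with a low-risk one, with or without the reverse swap in control.

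Example: at r = 2 and p = 30% the risks are 20% and 40%. Four swaps leave 9 high-risk and 17 low-risk patients, a mean of (9 × 0.40 + 17 × 0.20)/26 = 26.9%.

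Exact binomial results over r = 1.5 to 3:

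| True rates | Margin | No swaps | Two swaps | Four swaps |
|---|---|---|---|---|
| 30% v 10% | 20 points | 3.2–3.8% | +0.8 to +2.7 points | +1.7 to +7.1 points |
| 20% v 10% | 10 points | 3.5–3.9% | +0.6 to +2.2 points | +1.2 to +5.4 points |

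**5. Opportunity for swaps.** With all earlier allocations known, 17.3/2 = 8.7 places are certain no-touch, and half of these, 4.3, would hold a high-risk patient. Four or more arise in 64% of simulated lists. With the latest one unknown the average is 4.33/4 = 1.1, and four or more arise in 2% of lists.

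**6. Varied blocks.** I simulated lists with sizes 4, 6 and 8 drawn at random and redrawn until they sum to 52, for a recruiter who knows all earlier allocations and the set of sizes. Certain deductions are about 2% if the sum rule is unknown and about 5% if it is known. The best guess is right about 68% of the time. All lists end 26:26, and the running imbalance reaches 4 in about 8%.

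**The case against.** The strongest objection is that the 33% needs an observer whom the plan does not describe. Read literally, the statement that only the surgeon knows limits who holds the earlier allocations, and the person taking consent may hold none. The number of surgeons is not stated. If two or three share the cases and each knows only their own, the share is about 8.3% or 3.7% even before any delay between consent and surgery. This stands, and it is why the result is a range of averages from 0% to 33%. A reader might infer that a third of the assignments are predictable, but the documents do not support that.

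A reader might also infer that no concealment exists. The text is silent, and silence is not proof. Nor does the missing concealment create the 33%: opaque envelopes opened after consent would leave the deduction intact if blocks stay at four and earlier allocations are known.

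Third, one could measure the harm at the planning rates of 15% v 10%, where the effect looks larger. With r = 2, 26 per arm and a 20-point margin, the chance of declaring non-inferiority rises from 44.7% to 48.8–50.2% with two swaps and to 53.0–55.8% with four. A 5-point difference lies inside either margin, so these are gains in correct conclusions and not a measure of false ones.

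Finally, an opportunity is not a swap: steering needs a patient who can be deferred or declined and a suitable replacement. The four-swap figures belong essentially to the full-knowledge case. The recorded history and the planned multivariate analysis could reveal or adjust for measured factors, but not for unmeasured ones.

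**Conclusion.** The point holds as a design weakness that is cheap to remove. A single published block of four, in a single-centre trial where the team taking consent works with the one role that knows the technique, permits certain deduction of 33% of assignments on average at most. The share is 8% with the latest allocation unknown and 0% with two unknown or none known. The upper figure requires knowledge of the block size, the block boundaries and all earlier allocations, which the documents neither state nor exclude.

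The consequence for the conclusion is modest and illustrative. It rests on an assumed half of patients at high risk, an assumed risk ratio of 1.5 to 3, and swaps that nothing in the documents shows would occur. The change should be made. Confidence in the practical impact is medium.

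**What to change.** 1. Replace the fixed block of four with randomly varied sizes, for example 4, 6 and 8, redrawn until they sum to 52 so that 26:26 is kept. State in the protocol that block sizes vary at random, but keep the sizes and the sum rule out of it and away from the surgical team. This addresses deduction from earlier allocations.
2. State that each allocation is released only after eligibility and consent are recorded. Use sequentially numbered, opaque, sealed envelopes, or existing staff who are not recruiters, surgeons or blinded outcome assessors. The plan names no such person, so the role must be identified. This protects the list itself.

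The cost is one or two protocol sentences and a new computer-generated list. The downside bears on the plan's wish for similar numbers throughout: blocks of four hold the running imbalance to 2, whereas the varied blocks let it reach 4 in about 8% of lists. Without the sum rule about 28% of lists would end unequal. Neither measure removes better-than-chance guessing by someone who follows every allocation, since the best guess falls only from 71% to about 68%.
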